4.2.3 Handling of missing data for AE

For analyses of AEs, a complete date must be established to correctly identify the AE as occurring during treatment or not. For purposes of imputing missing components of partially reported start and stop dates for AEs, the algorithms listed below will be followed. In the event of ambiguity or incomplete data which makes it impossible to determine whether the AE was treatment emergent, the AE will be considered treatment emergent.

Although the algorithms for treatment-emergence depend on the onset date, imputation rules are provided for stop date as well, as these may be needed for certain statistical analyses, such as an analyses of AE prevalence or AE duration.

Start and stop dates of AEs will be displayed as reported in the subject data listings (ie, no imputed values will be displayed in data listings).

Imputation of Partial AE Start Dates

- If only the month and year are specified:
 - if the month and year of first dose of IMP is not the same as the month and year of the start date, then use the 1st of the month,
 - if the month and year of first dose of IMP is the same as the month and year of the start date, then use the date of first dose of IMP,
- If only the year is specified:
 - if the year of first dose is not the same as the year of the start date, then use January 1 of the year of the start date.
 - if the year of first dose is the same as the year of the start date, then use the date of first dose.
- If the date is completely unknown:
 - use the date of first dose of IMP if the stop date is unknown or not prior to the onset date.

Imputation of Partial Stop Dates:

- if only the month and year are specified, then use the last day of the month
- if only the year is specified, then use December 31st of that year
- if the stop date is completely unknown, then do not impute the stop date

If the imputed stop date is prior to the imputed start date:

- For missing start day and start month:
 - if the year of start date is the same as the year of first dose and the imputed stop date is on or after the date of first dose then set the start date to the date of first dose
 - otherwise set to the 1st January of the year of the start date

- For missing start day only
 - if the month and year of the start date is the same as the month and year of first dose and the imputed stop date is on or after the date of first dose, then set the start date to the date of first dose
 - if the month and year of the start date is the same as the month and year of first dose and the imputed stop date is before the date of first dose, then set the start date to the 1st of that month

In the event of ambiguity or incomplete data which makes it impossible to determine whether an AE is treatment emergent, the AE will be considered as treatment emergent.

Other imputations

In addition, the following will apply for presenting AE in summary tables:

- if the intensity of an AE is unknown, it will be considered as severe.
- if the relationship to study drug is missing, it will be considered as related.

For missing seriousness, no imputation rule will be applied.

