4.2.4 Handling of missing data for prior and concomitant medications

Any medications with incomplete start and end dates/times will be handled according to the following rules for classification as prior and concomitant and for the calculation of relative study days. In the event of ambiguity or incomplete data which makes it impossible to determine whether a medication was concomitant or not, the medication will be considered as concomitant. Such imputations will only be performed for these classifications and calculations; in the listings all data will be shown as recorded on the electronic case report form (eCRF).

Imputation of Partial Start Dates

- If only the month and year are specified:
 - if the month and year of first dose of IMP is not the same as the month and year of the start date, then use the 1st of the month.
 - if the month and year of first dose of IMP is the same as the month and year of the start, then use the date of first dose of IMP.
- If only the year is specified:
 - if the year of first dose of IMP is not the same as the year of the start date, then use the 1st of January of the year of the start date.
 - if the year of first dose of IMP is the same as the year of the start date, then use the date of first dose of IMP.
- If the start date is completely unknown:
 - if the stop date is unknown or not prior to the date of first dose of IMP, then use the date of first dose of IMP.
 - if the stop date is prior to the date of first dose of IMP, then set the start date to the 1st of January of the year of the end date.

Imputation of Partial Stop Dates:

- If only the month and year are specified, then use the last day of the month,
- If only the year is specified, then use December 31st of that year.
- If the stop date is completely unknown, do not impute the stop date. There will be no imputation of any other missing data.

If the imputed stop date is prior to the imputed start date:

- For missing start day and start month:
 - if the year of start date is the same as the year of first dose and the imputed stop date is on or after the date of first dose, then set the start date to the date of first dose
 - otherwise set to the 1st January of the year of the start date
- For missing start day only
 - if the month and year of the start date is the same as the month and year of first dose and the imputed stop date is on or after the date of first dose, then set the start date to the date of first dose

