10.2 Adverse events

An AE is any untoward medical occurrence in a patient or clinical investigation subject administered a pharmaceutical product that does not necessarily have a causal relationship with this treatment. An AE can therefore be any unfavorable and unintended sign (including an abnormal laboratory finding), symptom, or disease temporally associated with the use of a medicinal (investigational) product, whether related or not to the IMP.

AEs (including SAEs) are characterized as either non-treatment or treatment emergent according to the following criteria:

- Non-treatment emergent are the events with onset date and time prior to the very first administration of study medication (BKZ or placebo) or after a 140-day period after the final drug administration.
- Treatment-emergent AEs (TEAEs) are those with onset date at or after the very first administration of study medication. The events that emerge within 140 days after the final drug administration, will also be considered as treatment emergent (eg, in the case of premature discontinuation or during the 20-week SFU Period).

The incidence of TEAEs will be summarized descriptively by treatment group, MedDRA primary system organ class (SOC), high-level term (HLT), and preferred term (PT).

AEs will be presented as “number of subjects (percentage of subjects) [number of events]”. In this style of output, “[number of events]” will include all cases of an AE including repeat occurrences in individual subjects, while “number of subjects” will count each subject only once.

Adverse event summaries by SOC, HLT and PT will be ordered alphabetically for SOC and HLT within SOC and in terms of decreasing frequency for PT within HLT in the BKZ treatment group and then similarly by decreasing frequency in the placebo group.

AE summaries by PT will be ordered in terms of decreasing frequency for PT within the BKZ treatment group, and in the event of ties, PT will be sorted alphabetically.

TEAEs will be classified according to their date of emergence.

All summaries will be provided by treatment group on the SS.

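### The AE rule for a completely unknown start date tests the stop date against the AE's own unknown onset and has no branch for an event that ended before first dose

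*SAP*

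**What the plan says.** SAP Section 4.2.3 has one instruction for an AE with a completely unknown start date: "use the date of first dose of IMP if the stop date is unknown or not prior to the onset date". It does not say what to do otherwise.

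The same section makes onset the basis of classification ("Although the algorithms for treatment-emergence depend on the onset date"), and Section 10.2 defines the class: "Treatment-emergent AEs (TEAEs) are those with onset date at or after the very first administration of study medication". Section 4.2.3 then lists repairs for an imputed stop that falls before an imputed start. The cases named are "For missing start day and start month" and "For missing start day only". A closing default makes an AE treatment-emergent when its status cannot be determined.

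Section 4.2.4 treats the identical situation for medications in two branches. The first-dose date is used "if the stop date is unknown or not prior to the date of first dose of IMP". The other branch reads "if the stop date is prior to the date of first dose of IMP, then set the start date to the 1st of January", meaning 1 January of the stop year.

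**The concern.** A rule that fills in an unknown onset should not depend on that onset. Every other start-date bullet in Section 4.2.3, and the whole of Section 4.2.4, uses the first dose as the reference. This bullet alone does not, and it lacks the second branch that its counterpart has.

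At stake is the class of an AE with no recorded start and a recorded stop before first dose. Such an event cannot be treatment-emergent, yet the rule can place it on Day 1. TEAE incidence is a secondary safety variable (Section 2.2.2.2). A misplaced event would also enter the exposure-adjusted event rate. In the exposure-adjusted incidence rate (Section 10.2.3) it would cut that subject's exposure for the term to almost nothing. Section 10.2.2 calculates AE duration from the imputed start, so the duration would be negative.

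**Working it through.** There is no stated figure to reproduce; the check is to apply the rules to example records.

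**Inputs.** The AE rule is from Section 4.2.3, the medication rule from Section 4.2.4, the TEAE definition from Section 10.2, and the duration formula (end - start + 1) from Section 10.2.2. The dates are illustrative assumptions: first dose 15 March 2021, start completely unknown, five possible stops.

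**Reading the condition in 4.2.3.** The onset date could mean three things:

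1. The true onset. No stop can precede it, so nothing is excluded and the start becomes first dose.
2. The recorded onset. It is absent, so the test cannot be evaluated and no start is assigned.
3. The onset about to be imputed, that is, first dose. A pre-dose stop then fails the test, but the section gives no alternative start.

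None of the three leads to a stated pre-dose start.

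**Results under reading 1, beside the 4.2.4 form applied to AEs:**

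| Stop date | 4.2.3, reading 1 | 4.2.4 form |
|---|---|---|
| Unknown | start 15 Mar 2021, TEAE | same |
| 1 Apr 2021 | start 15 Mar 2021, TEAE, 17 + 1 = 18 days | same |
| 15 Mar 2021 | start 15 Mar 2021, TEAE, 0 + 1 = 1 day | same |
| 1 Mar 2021 | start 15 Mar 2021, TEAE, -14 + 1 = -13 days | start 1 Jan 2021, not TEAE, 59 + 1 = 60 days |
| 20 Dec 2020 | start 15 Mar 2021, TEAE, -85 + 1 = -84 days | start 1 Jan 2020, not TEAE, 354 + 1 = 355 days |

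The two rules differ only for the records that ended before first dose.

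**Do the listed repairs rescue these records?** They name a missing day, or a missing day and month, and they work from a start year or month that a wholly unknown date does not have. Suppose the day-and-month repair is stretched to this case, with the imputed year as the start year:

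- The 1 March record moves to 1 January 2021: not treatment-emergent, 60 days.
- The 20 December 2020 record also moves to 1 January 2021: not treatment-emergent, but -12 + 1 = -11 days.

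Stretching the repair therefore corrects the class in both examples but leaves a negative duration when the event ended in an earlier calendar year.

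**Does the ambiguity default apply?** It should not. A stop before first dose settles the status. Under readings 2 and 3, however, a programmer left with no start date could still fall back on it.

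**The case against.** The best defence is that the sentence is conditional, so it was meant to exclude something. Section 13.1 records that the AE rule once assigned the first-dose date without any condition and that Amendment 1 added the stop-date test. On that history, reading 3 is the likely intent, and an event that stopped before first dose was not meant to receive a first-dose start. This stands as evidence of intent. It also means that a reader who infers that the condition is always true, that every such record is misclassified, or that a negative duration is the certain output, goes further than the text allows. The condition may equally be unevaluable or refer to the imputed onset, and a programmer might stretch the day-and-month repair. None of this supplies the missing branch, and the stretched repair is not what the section says.

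A second objection is that the case hardly arises. Screening should last 14 to 35 days (Section 2.3.2), and conditions resolved before study entry are medical history (Section 6.3). A pre-dose AE with a recorded stop but not even a start year should therefore be very unusual. That stands, and it limits the importance of the point.

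A third is that 1 January of the stop year can put onset before consent. That also stands: 60 and 355 days in the examples exceed the longest planned Screening Period. It affects the duration of non-treatment-emergent events, not their class.

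**Conclusion.** The point holds as a drafting defect. The comparator in Section 4.2.3 is circular or ambiguous, the branch for a stop before first dose is missing, and Section 4.2.4 handles the same situation properly. An AE that ended before first dose can therefore be classed as treatment-emergent with a negative duration, depending on how the sentence is programmed.

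The size is small. The SAP gives no count of such records and no basis for estimating one, so a reader should not infer a material shift in TEAE incidence. No efficacy analysis uses the rule. The conclusion assumes only that an AE with a wholly unknown start and a recorded pre-dose stop can occur in the data. The worked dates are illustrations.

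**What to change.** In Section 4.2.3, for a completely unknown start date:

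- Make the comparator the date of first dose of IMP instead of the onset date.
- Add a branch: if the stop date is before first dose, assign a pre-dose start date and class the event as not treatment-emergent. The 4.2.4 convention, 1 January of the stop year, would serve.

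This costs one or two sentences and a small programming change that mirrors the medication rule. Records with a stop that is unknown, on or after first dose are unaffected. The downside is that the 1 January convention may overstate the duration of these non-treatment-emergent events; if that matters, another pre-dose date can be specified, provided it is not after the stop date.

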4.2.4 Handling of missing data for prior and concomitant medications

Any medications with incomplete start and end dates/times will be handled according to the following rules for classification as prior and concomitant and for the calculation of relative study days. In the event of ambiguity or incomplete data which makes it impossible to determine whether a medication was concomitant or not, the medication will be considered as concomitant. Such imputations will only be performed for these classifications and calculations; in the listings all data will be shown as recorded on the electronic case report form (eCRF).

Imputation of Partial Start Dates

- If only the month and year are specified:
 - if the month and year of first dose of IMP is not the same as the month and year of the start date, then use the 1st of the month.
 - if the month and year of first dose of IMP is the same as the month and year of the start, then use the date of first dose of IMP.
- If only the year is specified:
 - if the year of first dose of IMP is not the same as the year of the start date, then use the 1st of January of the year of the start date.
 - if the year of first dose of IMP is the same as the year of the start date, then use the date of first dose of IMP.
- If the start date is completely unknown:
 - if the stop date is unknown or not prior to the date of first dose of IMP, then use the date of first dose of IMP.
 - if the stop date is prior to the date of first dose of IMP, then set the start date to the 1st of January of the year of the end date.

Imputation of Partial Stop Dates:

- If only the month and year are specified, then use the last day of the month,
- If only the year is specified, then use December 31st of that year.
- If the stop date is completely unknown, do not impute the stop date. There will be no imputation of any other missing data.

If the imputed stop date is prior to the imputed start date:

- For missing start day and start month:
 - if the year of start date is the same as the year of first dose and the imputed stop date is on or after the date of first dose, then set the start date to the date of first dose
 - otherwise set to the 1st January of the year of the start date
- For missing start day only
 - if the month and year of the start date is the same as the month and year of first dose and the imputed stop date is on or after the date of first dose, then set the start date to the date of first dose
 - if the month and year of the start date is the same as the month and year of first dose and the imputed stop date is before the date of first dose, then set the start date to the 1st of that month

In the event of ambiguity or incomplete data which makes it impossible to determine whether a medication was concomitant, the medication will be considered as concomitant.

4.3 Interim analyses and data monitoring

4.3.1 Interim analysis

One interim analysis will be performed after all randomized subjects have completed the Double-Blind Treatment Period at Week 16.

The purpose of the Week 16 interim analysis is to perform a comprehensive evaluation of all available double-blind data for the BKZ and placebo treatment arms to prepare a regulatory submission for a Marketing Authorization Application based on this analysis.

The interim analysis will evaluate the primary and secondary efficacy variables as well as all other efficacy, safety and PK variable results up to Week 16. In addition, disposition, demographics and other Baseline characteristics, protocol deviations and compliance will be described. All available data at the time of the snapshot will be included (ie, even SFU data available beyond the Week 16 timepoint). Events on-going at the time of the interim analysis (eg, concomitant medications, adverse events) will be analyzed as they are collected to date, and analyses based on these events will be up to date at time of the final analysis.

For the interim analysis, the database will be locked, and the treatment codes will be made available to UCB personnel. An interim report will be written. The investigators and subjects will remain blinded to the assigned BKZ dosing regimen until the final analysis is completed. A blinding maintenance plan will be written to evaluate the potential bias in data reporting and

describe the process of interim results generation and dissemination. The plan will be finalized prior to the lock of the database at the interim analysis.

No formal alterations to the further study conduct (eg, stopping rules, sample size re-estimation, or changes to eligibility criteria) are planned for the interim analysis.

No separate SAP for the interim analysis will be provided. The TFL shells for the interim and final analyses will be provided in the same document. The final analysis will consist of a re-run of all analyses, including new data occurring during the SFU Period that were not available for the interim Week 16 analysis.

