The SFU Period will be defined for all subjects who complete the study and do not enter the OLE study, or for subjects who discontinue early including those withdrawn from IMP. This period should last 20 weeks from the final dose.

- For subjects who complete the study and do not enter the OLE study, the SFU Period starts the day after Visit 6 date and ends on the day of the SFU Visit.
- For subjects who discontinue early, the SFU Period starts the day after the ET date and ends on the day of the SFU Visit

A subject will be considered to have completed a study period if they complete the last scheduled study visit for that period. Note that subjects who previously discontinued IMP and are continuing for all scheduled visits through Week 16 will also be considered as completed the Double-Blind Treatment Period.

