7 MEASUREMENTS OF TREATMENT COMPLIANCE

Treatment compliance summaries will be performed based on the SS, by randomized treatment and for all subjects.

Due to the method of administration of the treatments, compliance will be examined in terms of completed injections. Treatment compliance will be calculated as:

$$\frac{\text{Total number of actual (completed) injections}}{\text{Total number of expected injections}} \times 100\%$$

The total number of expected injections is derived relative to when the subject finishes treatment.

If a subject completes treatment, 4 injections are expected (at Baseline, Week 4, Week 8 and Week 12).

If a subject discontinues early, then the number of expected injections is based on the time of early discontinuation relative to the dosing visits. This number will be calculated by determining the number of expected dosing visits prior to the date of early discontinuation. If the early discontinuation coincides with an expected dosing visit, this visit will be used to determine the number of expected injections.

A summary of percent treatment compliance categorized as <75% and ≥75% will be provided by treatment group, as well as a by-subject listing of treatment compliance.

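### Crude BKZ and placebo safety percentages mix follow-up to Week 16 with follow-up to as late as Week 32, and no adverse event or worst-value laboratory table is limited to the 16-week placebo-controlled period

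*SAP*

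**What the plan says.** **Scope and data of the interim.** Section 4.3.1 of the SAP gives the scope as efficacy, "safety and PK variable results up to Week 16". Shortly afterwards it says: "All available data at the time of the snapshot will be included (ie, even SFU data available beyond the Week 16 timepoint". The final analysis extends this: "The final analysis will consist of a re-run of all analyses, including new data occurring during the SFU Period".

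**Event window and tables.** Section 10.2 sets the window: "The events that emerge within 140 days after the final drug administration, will also be considered as treatment emergent". It also says: "All summaries will be provided by treatment group on the SS". None of the tables listed in Section 10.2.1 is limited to the Double-Blind Treatment Period. Section 2.3.2 defines study periods and Section 10.2 says TEAEs are classified by date of emergence, but the only period split of adverse events is by COVID-19 pandemic period (Section 10.2.5). In Section 10.3, minimum and maximum post-Baseline laboratory values and markedly abnormal values likewise run to 140 days after the last dose.

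**Who is followed beyond Week 16.** Section 2.3.2: "The SFU Period will be defined for all subjects who complete the study and do not enter the OLE study", and also for subjects who discontinue early. On length: "This period should last 20 weeks from the final dose".

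**Exposure adjustment.** Sections 10.2.1 and 10.2.3 plan EAIR (with 95% CI) and EAER for TEAEs by SOC/HLT/PT, TEAEs leading to study or drug discontinuation, the ADAb and NAb tables, and TESAEs. Section 10.2.4 adds them for the safety topics of interest. They are not listed for the overview, maximum intensity, relationship, the 5% threshold tables or deaths, and they do not apply to worst laboratory values.

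**The concern.** A reader of the interim report would take the BKZ and placebo percentages as incidences over the 16-week placebo-controlled period, because that is the stated scope. They are not. They are incidences over whatever time each subject was followed, and that time depends on a choice made after randomization, namely whether to enter the OLE. That choice may be related to response or tolerability.

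If more placebo than BKZ subjects decline the OLE, placebo percentages rise and a BKZ excess is partly hidden. The reverse imbalance produces an apparent excess. Even with balance, the percentages are higher than true 16-week values, and the interim and final figures for the same table differ only because more SFU has accrued. Section 4.3.1 says the interim analysis is meant to support a marketing application, so the displays should match their description.

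**Working it through.** **1. Length of follow-up.** The last planned dose is at Week 12 (Section 7: "4 injections are expected (at Baseline, Week 4, Week 8 and Week 12"). Adding 140/7 = 20 weeks gives 12 + 20 = Week 32. As a check, maximum Screening of 35/7 = 5 weeks plus 12 plus 20 gives 37 weeks, which reproduces the maximum study duration in Section 2.3.1.

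- OLE entrants: time at risk ends at the last visit, Week 16 (Section 10.1.1).
- Completers who decline the OLE: up to Week 32.
- Early discontinuers with last dose at Week 0, 4 or 8: up to Week 20, 24 or 28.
- At the interim, all of the SFU limits are upper limits, since SFU may still be running.

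**2. Effect on crude incidence.** The SAP gives neither event incidence nor OLE non-entry, so both are assumed over a range. Let I be the 16-week incidence and s the share of an arm followed to Week 32, with the same constant hazard in both arms and no true difference. Incidence by Week 32 is 1 − (1 − I)². Then

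crude incidence = (1 − s)·I + s·[1 − (1 − I)²] = I + s·I·(1 − I)

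spurious difference = (difference in s between arms)·I·(1 − I)

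| I (16 weeks) | by Week 32 | crude, s = 5% | crude, s = 10% | crude, s = 20% | artefact, 5% vs 10% | artefact, 5% vs 20% |
|---|---|---|---|---|---|---|
| 2% | 3.96% | 2.10% | 2.20% | 2.39% | 0.10 points | 0.29 points |
| 5% | 9.8% | 5.24% | 5.48% | 5.95% | 0.24 | 0.71 |
| 20% | 36% | 20.8% | 21.6% | 23.2% | 0.8 | 2.4 |
| 40% | 64% | 41.2% | 42.4% | 44.8% | 1.2 | 3.6 |
| 50% | 75% | 51.25% | 52.5% | 55.0% | 1.25 | 3.75 |

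With equal s the artefact between arms is 0, but both arms move: at I = 40% and s = 10%, each shows 42.4% instead of 40.0%.

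**3. Effect on EAIR.** Under the same constant hazard h, a subject followed for time T has expected event count 1 − exp(−hT) and expected time to event or end of follow-up [1 − exp(−hT)]/h. The ratio is h for every T and so for any mix of T. The planned EAIR carries no artefact under this model.

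**4. After a cut at Week 16.** Every completer contributes 16 weeks, and the spurious difference is 0 under the model.

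**The case against.** The strongest answer is that the SAP already handles unequal follow-up where it matters most. Section 10.1.1 defines time at risk separately for OLE entrants and all others, expressly including subjects still in SFU at the snapshot, so numerator and denominator stay matched. EAIR and EAER are then attached to the main TEAE, discontinuation, TESAE and safety-topic tables. The 140-day window is deliberate, tied to five half-lives of BKZ, and applied to both arms. Safety is summarised descriptively, with no between-arm test planned. The inclusion of SFU data is stated openly in Section 4.3.1, so the programming rule is clear even if the scope sentence is loose.

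All of this stands, and it confines the point to crude percentages and to displays without EAIR.

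A reader might go further and infer that the EAIRs are themselves distorted, or that a BKZ excess will be masked. The documents support neither. Under constant hazards the EAIR is unaffected (step 3). If event rates fall or rise after dosing stops, EAIR averages over both phases, but the SAP gives nothing to show that they do. Masking needs more placebo than BKZ subjects to decline the OLE, and the SAP contains no such indication. Nor is the 140-day definition an error.

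**Conclusion.** The point holds in limited form. The stated Week 16 scope in Section 4.3.1 does not match the data included, and nothing in Sections 10.2.1 or 10.3 supplies a crude adverse event or worst-laboratory comparison over the placebo-controlled period. The affected results are the crude percentages throughout, and above all the displays with no exposure adjustment: overview, intensity, relationship, 5% threshold, deaths, and minimum/maximum laboratory values.

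Size and direction cannot be determined from the SAP. The range of about 1 to 4 points for common events (16-week incidence of 20% to 50%) rests on an assumed equal constant hazard, on assumed non-entry of 5% in one arm and 10% or 20% in the other, and on all non-entrants being followed to Week 32. For rare events it is a few tenths of a point or less. This is a presentation gap worth closing before the database lock, not a flaw that invalidates the safety analysis.

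**What to change.** In Sections 4.3.1 and 10.2.1, with a matching line in 10.3, state that at both interim and final the crude BKZ and placebo tables for TEAEs, TESAEs, discontinuations, safety topics and worst laboratory values are also produced for onset or assessment from first dose through the Week 16 visit.

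For subjects without a Week 16 visit, use the scheduled Week 16 date and count any events collected up to then. Do not stop at the ET visit, since that would shorten the window for early withdrawals and drop their later events.

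Show later SFU-onset events in a separate table for subjects who entered the SFU Period. Keep the planned 140-day TEAE tables with EAIR and EAER as the overall presentation, and reword the scope sentence in 4.3.1 to name both sets. The SAP already reports overall ADAb and NAb status with and without SFU (Sections 9.2.1 and 9.2.2), so the device is familiar.

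The cost is one period flag in the adverse event and laboratory programs and some extra tables. No new data are needed. Subjects lost before Week 16 will still have shorter observation, which the EAIR tables continue to address.
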